3.2 Inclusion-Exclusion Criteria and General Study Population

All emergency calls received at the Emergency Medical Dispatch Center and handled by either the intervention or control group will be included in the study.

Inclusion criteria

- Emergency calls (1-1-2 calls equivalent to 9-1-1 calls),
- Received by an EMS dispatcher included in the study (intervention or control group/cluster).

Exclusion criteria

- All calls to the EMDC other than emergency calls (including those from hospitals and general practitioners, including those outside of regular hours),
- Emergency calls managed by EMS dispatchers who are newly employed within the study period, on long-term leave, or not employed until the end of the study period are excluded from the study,

• Emergency calls managed by technical dispatchers (logistical dispatcher restricted to dispatching only the highest urgency level).

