2.3 Study setting and cluster design

In the Central Denmark Region, a single Emergency Medical Dispatch Center (EMDC) handles all emergency calls (equivalent to 9-1-1 calls in the US). The region receives approximately 55,000 to 60,000 emergency calls annually and employs around 25 Emergency Medical Service (EMS) Dispatchers, all of whom are either nurses or paramedics. Within the EMDC, EMS dispatchers were divided into one of two clusters, each containing 10 EMS dispatchers. Due to the limited number of clusters, a matched-pair (MP) design was adopted. This design relied on specific criteria for matching, including the average proportion of dispatched urgency levels (with the highest urgency level as the primary criterion), years of employment, and the average call duration. The data used for matching covered a 3-month period from January 1, 2022, to March 31, 2022, both prior to the introduction of video streaming and preceding the pilot phase of the study.

Newly employed personnel where matching was not possible were randomly assigned to one of the two clusters. Before the study period, the implementation of video streaming in the intervention group occurred progressively over a span of 7 months (from June 1, 2022, to December 31, 2022), following a pilot phase that took place from April 19, 2022, to May 31.

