3.1 General Study Design and Plan

Study type: Single center, prospective, cluster-randomized, unblinded trial.

Type of Comparison: superiority

Type of control: Matched control group (matched-pair design)

Randomization: Emergency calls received in the Emergency Medical Dispatch Center are allocated

randomly between the intervention group and the control group. Given the extended call duration

within the intervention group, it is anticipated that the control group (telephone-only) will experience

a higher volume of calls.

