3.3 Randomization

Emergency calls will be allocated at random to either of the two clusters: the intervention group utilizing video, or the control group utilizing telephone-only communication. Alternatively, some emergency calls will be directed to EMS dispatchers who are not part of the study.

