3.6 Analysis Populations

Intention to Treat (video stream)

The intention-to-treat populations (intension-to-video-stream) includes all patients allocated to either exposure group. Binary outcomes are investigated using risk differences (RD) implementing linear regression and relative risks (RR) by Poisson regression. Robust variance estimation is applied in both regression analyses. Continuous outcomes are investigated using linear and Tobit regression, where the latter is implemented for time variables that are right censored. Time-to-event variables are SAP version 1.0: CAM-VISION 18.08.2023 Page 6 of 7

investigated using Cox-regression analysis, while CPC and mRS are investigated using ordered logistic regression and by the concordance index. To account for cluster randomization, we will implement cluster robust variance in all regression analyses with a separate cluster id for each EMS dispatcher. Effect measures are presented with 95% confidence intervals and all analyses are conducted in Stata 17.

No per-protocol analyses will be conducted because of substantial risk of selection bias.

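### Dropping every call handled by a dispatcher who later leaves makes inclusion depend on a post-allocation event, at odds with the SAP's intention-to-treat set

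*SAP*

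**What the plan says.** Section 3.2 opens by including all emergency calls handled by either group. Its exclusion list then takes out calls by an attribute of the dispatcher who managed them: hired during the study period, on long-term leave, or "not employed until the end of the study period are excluded from the study". No date limits the last two grounds.

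Section 3.3 describes allocation at the level of the call: "Emergency calls will be allocated at random to either of the two clusters". It adds that "some emergency calls will be directed to EMS dispatchers who are not part of the study".

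The clusters predate the study period. Section 2.3 describes two clusters, "each containing 10 EMS dispatchers", and states: "Before the study period, the implementation of video streaming in the intervention group occurred progressively over a span of 7 months". The study period runs from 1 January to 30 April 2023 (section 2.2).

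Section 3.6 defines an intention-to-treat population that "includes all patients allocated to either exposure group", with no exception for leavers. It also states: "No per-protocol analyses will be conducted because of substantial risk of selection bias". No sensitivity analysis brings the excluded calls back.

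**The concern.** Take a cluster dispatcher who answers calls from January to March 2023 and leaves in April. Each call was allocated when it came in, yet section 3.2 deletes all of them because of the April departure. An exclusion after randomisation is defensible when it rests on facts fixed before allocation. Staying in post until 30 April is not such a fact. The ground concerning new hires is different, because that status is known before any of their calls is allocated; it is not criticised here.

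Three features of the trial make this relevant to the primary comparison:

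- Section 3.1 describes a "Single center, prospective, cluster-randomized, unblinded trial", so dispatchers know their arm, and leaving could in principle be related to it.
- The dispatcher sets the urgency level, and the highest level (A) is the primary outcome.
- There are only about 10 dispatchers per arm, and each is a cluster in the variance estimate (section 3.6). Dropping one removes a whole cluster, from groups that were matched primarily on the proportion of highest-urgency dispatches.

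**Working it through.** **Texts side by side**

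1. Section 3.3: a call is allocated on receipt.
2. Section 2.3: the cluster to which it goes was formed before the study period.
3. Section 3.2: the call is kept only if its dispatcher is still employed on 30 April 2023.
4. Section 3.6: everyone allocated is in the intention-to-treat set.

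Given steps 1 and 2, steps 3 and 4 cannot both hold for calls handled before a departure. Treating leavers as dispatchers outside the study, as section 3.3 might allow, does not help, because their membership would still be decided by the later event. For long-term leave the SAP gives no onset date, so that ground is at issue only if leave began during the period.

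**The plan's own call count**

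Section 2.3 gives 55,000 to 60,000 calls a year. Over 4 of 12 months this is 18,333 to 20,000; over 120 of 365 days it is 18,082 to 19,726. Section 3.4's 18,000 to 20,000 is therefore the whole centre's volume, before non-study dispatchers or these exclusions are taken off.

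**Size of the effect (illustration)**

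From the SAP: 18,000 to 20,000 calls, around 25 dispatchers, 10 per cluster. Assumed: equal workload; one leaver; the leaver's A-rate differs by D = 5 to 10 points from the mean of the other nine; between-dispatcher SD of 5 points; overall A-rate p of 0.3 to 0.5; about 750 calls per dispatcher.

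- Calls in the two clusters: 18,000 to 20,000 × 20/25 = 14,400 to 16,000. Per dispatcher: divided by 20 = 720 to 800.
- With f the fraction of the period worked, the leaver's share of the arm is w = f/(9 + f), and the shift in the arm's A-rate is D × w.
- Standard error of the arm difference, in points: √[2 × (5² + 10⁴ × p(1−p)/750)/10]. For p = 0.3 this is √5.56 = 2.36; for p = 0.5 it is √5.67 = 2.38. I use 2.37.

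| f | Calls lost | Share of arm | Shift, D = 5 to 10 (points) | Shift / SE |
|---|---|---|---|---|
| 0.25 | 180 to 200 | 2.7% | 0.14 to 0.27 | 0.06 to 0.11 |
| 0.5 | 360 to 400 | 5.3% | 0.26 to 0.53 | 0.11 to 0.22 |
| near 1 (upper bound) | 720 to 800 | 10% | 0.5 to 1.0 | 0.21 to 0.42 |

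If the whole shift were bias of b standard errors, a nominal 95% interval would cover with probability Φ(1.96 − b) − Φ(−1.96 − b). For b = 0.222 this is 94.4%; for b = 0.422 it is 92.9%.

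**Sensitivity to the assumptions**

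- If ten dispatchers remain after the exclusion, w = f/(10 + f), and the half-period shift is 0.24 to 0.48 points.
- With a between-dispatcher SD of 2.5 the SE is 1.35 to 1.38, and the half-period, 10-point case is 0.38 to 0.39 SE. With an SD of 10 the SE is 4.53 to 4.55, and the same case is 0.12 SE.
- If the 20 study dispatchers took all 18,000 to 20,000 calls, each would handle 900 to 1,000. The share of the arm and the shift would not change.

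**The case against.** The best defence is that the two sections can be read together. Section 3.2 admits only calls received by a dispatcher included in the study, so the intention-to-treat set might mean all allocated calls among eligible dispatchers. The rule is the same in both arms, does not depend on whether video was used, and was written before data extraction. A fixed roster is also a recognisable choice when clusters were built by matching dispatchers. The combined reading does not resolve the problem, because eligibility would still turn on a later event. Writing the rule before extraction guards against an outcome-driven choice, but it does not turn later employment into a baseline fact.

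Several points on that side do stand:

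- The SAP does not say when leaver status was determined. Some departures may have been known before 1 January 2023, and the 10 per cluster may already be a roster net of exclusions. The fix below allows for status fixed in advance.
- The per-protocol analysis that section 3.6 rejects most naturally means selecting calls by actual video use. The parallel with a completers-only roster supports the argument but does not carry it.
- The illustration is built on assumptions. With an SD of 5, a 10-point gap from nine colleagues is already about 1.9 SD of such a gap (5 × √(1 + 1/9) = 5.27; 10/5.27 = 1.9). With an SD of 2.5 it is about 3.8 SD (10/2.64), so the 0.38 SE result deserves little weight.

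**Conclusion.** The concern holds. As written, the rule removes calls after random allocation because of a subsequent event, and it contradicts both the stated intention-to-treat set and section 3.2's own opening statement. This rests on the wording, not on a demonstrated bias.

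The practical effect is probably modest. It is nil if nobody left, and it can bias the A-response comparison only if leaving is related to arm. For one leaver under the stated assumptions, the half-period case with a 10-point gap gives 94.4% coverage even if the entire shift is bias. The upper bound of 92.9% needs a leaver who worked nearly the whole period. The actual loss cannot be computed, because the SAP gives neither the number nor the arm of leavers. It should be fixed because the correction is simple and removes an avoidable route to selection bias.

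**What to change.** Amend sections 3.2 and 3.6 as follows:

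- In the primary intention-to-treat analysis, keep in the assigned arm all eligible calls handled by dispatchers who belonged to a cluster at the start of the study period, up to departure, and up to the start of leave if leave began during the period.
- Limit the employment and leave exclusions to status fixed before the study period, and state the date on which cluster membership was closed.
- Report departures, leaves and affected calls by arm.
- Present the completers-only set as a sensitivity analysis.

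The cost is a change of wording and one extra analysis. Section 3.5 says extraction had not begun and authorisation was pending, but not whether its scope can still change, so a wider data request may be needed. Cluster sizes become slightly more uneven. Keeping these calls does not replace the dispatcher after departure; it only stops later employment deciding whether earlier calls count.

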3.3 Randomization

Emergency calls will be allocated at random to either of the two clusters: the intervention group utilizing video, or the control group utilizing telephone-only communication. Alternatively, some emergency calls will be directed to EMS dispatchers who are not part of the study.

3.4 Sample Size

The CAM-VISION trial is conducted using a convenience sample, with an anticipated count of emergency calls during the study period ranging between 18,000 and 20,000.

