2.2. Study period

The study will be conducted from January 1, 2023, to April 30, 2023.

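### Does section 3.4 overstate the trial's sample by giving the whole dispatch centre's call volume?

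*SAP*

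**What the plan says.** Under the heading Sample Size, SAP section 3.4 has one sentence. The trial is "conducted using a convenience sample, with an anticipated count of emergency calls during the study period ranging between 18,000 and 20,000". It gives no power, effect size, intracluster correlation or target interval width.

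The figures behind the range are elsewhere in the SAP. Section 2.2 fixes the period: "The study will be conducted from January 1, 2023, to April 30, 2023". Section 2.3 says that one centre takes all emergency calls in the region, and gives its volume and staffing: "The region receives approximately 55,000 to 60,000 emergency calls annually and employs around 25 Emergency Medical Service (EMS) Dispatchers". The same section says that "EMS dispatchers were divided into one of two clusters, each containing 10 EMS dispatchers", and adds: "Newly employed personnel where matching was not possible were randomly assigned to one of the two clusters".

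Eligibility is in section 3.2: calls "handled by either the intervention or control group will be included in the study". That section removes calls taken by technical dispatchers, and by dispatchers hired during the period, on long-term leave or gone before its end. Section 3.3, directly before the sample-size section, says that some calls reach dispatchers who take no part in the study.

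**The concern.** A number under the heading Sample Size, in the same sentence as the sampling method, is naturally read as the number of calls the trial expects to analyse. Here it equals every emergency call the centre would receive in four months, although the design takes only those handled by the two clusters. Section 3.4 neither says that the figure is centre volume nor deducts anything for calls handled elsewhere.

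If a power or precision statement had been built on the range, it would have been too favourable. Even without one, a reader who later compares the reported number of calls with the SAP could see an unexplained shortfall that is only the planned exclusions at work.

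**Working it through.** **Inputs from the SAP.** Annual centre volume 55,000 to 60,000 (section 2.3). Study period 1 January to 30 April 2023 (section 2.2): 31 + 28 + 31 + 30 = 120 days, or 4 months. Stated range 18,000 to 20,000 (section 3.4). About 25 dispatchers, of whom 2 × 10 = 20 are in clusters (section 2.3).

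**Reproducing the stated range.** Centre volume in the period = annual volume × fraction of the year.

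- By months: 55,000 × 4/12 = 18,333; 60,000 × 4/12 = 20,000.
- By days: 55,000 × 120/365 = 18,082; 60,000 × 120/365 = 19,726.

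Both ends agree with 18,000 and 20,000 to within rounding, with no deduction. The SAP does not show its derivation, so this is an inference, but it holds at both ends and by both methods.

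**Direction of the gap.** Section 3.3 says some calls go outside the study, so included calls = centre volume × *s*, where *s* is the study dispatchers' share and is below 1. The included count is lower than centre volume.

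**Size of the gap.** The SAP does not give *s*. One percentage point of *s* is worth 18,082 × 0.01 ≈ 181 calls at the low end and 20,000 × 0.01 = 200 at the high end. The included count reaches the bottom of the stated range, at the highest annual volume, when *s* = 18,000/20,000 = 0.90 (months) or 18,000/19,726 ≈ 0.91 (days).

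The shares below are assumptions. The low end uses 18,082 and the high end 20,000.

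| Assumed *s* | Included calls |
|---|---|
| 0.80 (20 of 25, calls in proportion to head count) | 14,466 to 16,000 |
| 0.90 | 16,274 to 18,000 |
| 0.95 | 17,178 to 19,000 |

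The SAP does not select a row. Calls need not follow head count. Section 3.1 itself says that "it is anticipated that the control group (telephone-only) will experience" the larger call volume, so load differs even between the clusters. Staff on long-term leave may take few calls, which would raise *s*; calls to technical dispatchers lower it by an amount not given.

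**What uses the number.** Nothing in the SAP takes 18,000 to 20,000 as an input. Section 3.6 estimates effects from the allocated calls, with variance clustered on the dispatcher, so interval width will depend on the observed calls and on variation between dispatchers.

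**Timing.** The SAP carries the date 18 August 2023, which is 31 + 30 + 31 + 18 = 110 days after 30 April and so past the longest listed follow-up of 90 days. Section 3.5 agrees that the study and follow-up periods were complete at drafting.

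**The case for a change.** The strongest case for a change is that this is the only size figure in the SAP, it stands in the section meant for it, and it is in the wrong role. A correct number with the wrong label still misleads, and a label would cost one clause. Sections 3.2 and 3.3 state the exclusions but do not connect them to the number.

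Much of this stands. The range is centre volume, the included sample is smaller, and section 3.4 does not say so.

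What does not stand is that it matters for the trial. The sentence speaks of emergency calls in the period, not of included or analysed calls, and in that sense it is accurate. The restriction to study dispatchers is in the two sections immediately before it, so an analyst could not take the wrong population.

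Asking for a new forecast of included calls would also gain nothing. Intake was over, and the true count will be known once data are extracted. The obvious source may not even hold what is needed: "The data used for matching covered a 3-month period from January 1, 2022, to March 31, 2022", but the matching criteria listed are urgency proportions, years of employment and call duration, with no mention of call counts.

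**Conclusion.** The observation is right and the consequence is nil. The 18,000 to 20,000 in section 3.4 is the centre's four-month volume, and the included sample is smaller by about 181 to 200 calls for each percentage point of calls handled outside the clusters. The total shortfall cannot be read from the SAP; a figure such as 20% rests on the assumption that calls follow head count.

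No change to the plan is called for. With a convenience sample, no sizing calculation and intake closed, a different anticipated count would alter neither enrolment, nor the analysis, nor any conclusion the trial can draw. This is a labelling slip that the neighbouring sections already resolve for a careful reader, and the reported number of included calls will settle it. The conclusion assumes that no power or precision statement elsewhere, for instance in a protocol not seen here, uses this range as the analysed number.

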3.5 Timing of Analyses

The study period and its corresponding follow-up periods, as determined by specific variables, are finalized during the drafting of this SAP (Statistical Analysis Plan).

As of this SAP, data extraction has not been initiated due to pending data authorization. The subsequent actions, in chronological order, prior to data extraction and analysis, are outlined below:

SAP Signature

• By the principal investigator and the senior statistician.

Data Authorization

- The Regional Research Council (The Legal Office, Central Denmark Region) and
- The Danish Data Protection Agency.

Primary Analyses

• Primary and Secondary Outcomes

Secondary analyses

Other Outcomes

3.6 Analysis Populations

Intention to Treat (video stream)

The intention-to-treat populations (intension-to-video-stream) includes all patients allocated to either exposure group. Binary outcomes are investigated using risk differences (RD) implementing linear regression and relative risks (RR) by Poisson regression. Robust variance estimation is applied in both regression analyses. Continuous outcomes are investigated using linear and Tobit regression, where the latter is implemented for time variables that are right censored. Time-to-event variables are SAP version 1.0: CAM-VISION 18.08.2023 Page 6 of 7

investigated using Cox-regression analysis, while CPC and mRS are investigated using ordered logistic regression and by the concordance index. To account for cluster randomization, we will implement cluster robust variance in all regression analyses with a separate cluster id for each EMS dispatcher. Effect measures are presented with 95% confidence intervals and all analyses are conducted in Stata 17.

No per-protocol analyses will be conducted because of substantial risk of selection bias.

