2.4 Endpoints

Primary Outcome Measure

• The frequency of dispatches with the highest level of urgency (A-responses)

Secondary Outcome Measures

- The frequency of dispatches with the levels of urgency A, B, C, D and E,
- Mortality within 30 days after study inclusion,
- Number of participants where the levels of urgency are identical when comparing the ambulance

to and from the scene,

SAP version 1.0: CAM-VISION

- Length of stay at hospital,
- The number of participants needing an ICU admission at hospital,
- Number of emergency calls where the dispatched level of urgency is changed during the call,
- Number of emergency calls where the initially dispatched level of urgency is subsequently lowered,
- Number of emergency calls where the initially dispatched level of urgency is subsequently increased,
- Number of emergency calls where the allocated resources is changed during the call,
- Number of participants readmitted to hospital within 24 hours after a dispatch without hospital admission (lowest level of urgency response level E),
- Duration of emergency medical calls,
- Time from emergency call to dispatch,
- On-scene time

Other Pre-specified Outcome Measures:

- Number of participants with return-of-spontaneous circulation (ROSC) after cardiac arrest
- 90 days neurological outcome after cardiac arrest measured by the cerebral performance scale (CPC)
- 90 days functional outcome after cardiac arrest measured by the modified Rankin Scale (mRS)
- Number of patients with Stroke or TIA identified by the EMS dispatcher in the EMDC
- Rate of revascularization treatment (intravenous thrombolysis and/or endovascular treatment (EVT)) among patients with acute ischemic stroke
- Primary admission to a hospital offering acute stroke treatment
- Onset-to-treatment times for patients with acute ischemic stroke treated with i.v. thrombolysis and onset-to-groin-puncture for patients treated with EVT.
- Number of lowest level of urgency (response level E) dispatched among children (< 15 years

of age)

SAP version 1.0: CAM-VISION

- Re-admissions among children (< 15 years of age) to hospital within 24 hours from a prior emergency call dispatched with lowest level of urgency (response level E)
- Number of dispatches for each level of urgency (response level A, B, C, D and E) among children (< 15 years of age)

3 Study Methods

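### SAP section 3.6 names no patient covariate for 30-day mortality; prespecifying age would give a small, low-cost gain in precision, though the unadjusted analysis is valid

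*SAP*

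**What the plan says.** For binary outcomes, SAP section 3.6 states: "Binary outcomes are investigated using risk differences (RD) implementing linear regression and relative risks (RR) by Poisson regression". It adds that "we will implement cluster robust variance in all regression analyses with a separate cluster id for each EMS dispatcher" and that "Effect measures are presented with 95% confidence intervals". It also lists Tobit, Cox and ordered logistic models for other types of outcome. No adjustment covariate is named for any of them.

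Section 2.4 lists "Mortality within 30 days after study inclusion" as a secondary outcome. Section 3.6 does not say whether it is treated as binary or as time-to-event. Patient age enters only through outcomes such as "Number of dispatches for each level of urgency (response level A, B, C, D and E) among children (< 15 years of age", so at least the split at 15 years must be available.

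On allocation, section 3.3 says "Emergency calls will be allocated at random to either of the two clusters". Section 3.1 says "it is anticipated that the control group (telephone-only) will experience" more calls, because calls in the video group last longer. Section 2.3 matches dispatchers on dispatcher characteristics only. Section 3.5 says that data extraction had not begun when the SAP was written.

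**The concern.** Whether a patient dies within 30 days depends heavily on age. A model that omits age leaves that variation in the residual, and the interval for the effect of video is wider than it needs to be. Age is set before the call and video cannot change it, so adjusting for it cannot introduce post-allocation bias. For a risk difference or a relative risk, adjustment also leaves the estimated quantity unchanged.

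The primary outcome concerns how urgently calls are dispatched. If video changes that, 30-day mortality is one of the outcomes a reader will use to judge whether patients were affected, and the width of its interval decides what can be excluded. The sample is a convenience sample with no power calculation, so precision can be improved only through the analysis. A covariate chosen after the data are seen would carry less weight than one fixed beforehand.

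**Working it through.** **1. The plan's own figure.** 1 January to 30 April 2023 is 120 days. From the annual volume in section 2.3, 55,000 × 120/365 = 18,082 and 60,000 × 120/365 = 19,726. This reproduces the 18,000–20,000 calls of section 3.4. It is the region's whole volume, and some calls go to dispatchers outside the study. With 20 of about 25 dispatchers and equal call shares, 18,000 × 20/25 = 14,400. The smaller number widens every interval below but leaves the percentage gains unchanged.

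**2. Assumptions (none are in the SAP).**
- 18,000 calls split 45:55, that is 8,100 and 9,900.
- Mortality of 2–6%.
- A logistic relation between age and death, with an odds ratio of 1.3–2.2 per 10 years.
- Age with mean 55 years and SD about 23 years, limited to 0–100.

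**3. Formulas.** Unadjusted half-width = 1.96 × √[p(1−p)(1/n₁ + 1/n₂)]. Adjusted half-width = unadjusted × √(1−R²), where R² is the share of the variance in death that age explains. Calls are treated as independent.

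**4. Central case: 4% mortality, odds ratio 1.9.**
- Unadjusted: 1.96 × √[0.04 × 0.96 × (1/8,100 + 1/9,900)] = 0.575 percentage points.
- Linear age, R² = 0.053: 0.560 points, 2.7% narrower, worth 1/(1−0.053) = 1.06 times the calls.
- Flexible age, R² = 0.081: 0.552 points, 4.1% narrower, worth 1/(1−0.081) = 1.09 times the calls.

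**5. Range for mortality.**

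| Mortality | OR per 10 years | Unadjusted half-width (points) | Linear age | Flexible age | Narrower by |
|---|---|---|---|---|---|
| 2% | 1.3 | 0.411 | 0.410 | 0.410 | 0.3–0.4% |
| 2% | 2.2 | 0.411 | 0.404 | 0.398 | 1.8–3.3% |
| 4% | 1.3 | 0.575 | 0.572 | 0.571 | 0.6–0.7% |
| 4% | 2.2 | 0.575 | 0.556 | 0.541 | 3.4–6.0% |
| 6% | 1.3 | 0.697 | 0.691 | 0.690 | 0.9–1.0% |
| 6% | 2.2 | 0.697 | 0.662 | 0.639 | 5.0–8.3% |

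A second assumed age distribution (10% uniform on 0–15 years, 90% normal with mean 58 and SD 22) gave R² from 0.034 (3% mortality, odds ratio 1.6) to 0.185 (6%, odds ratio 2.4). The interval is then 1−√(1−0.034) = 1.7% to 1−√(1−0.185) = 9.7% narrower.

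**6. Check with clustering.** Trials were simulated with 20 dispatchers, 5% mortality, a dispatcher log-odds SD of 0 or 0.1, and cluster-robust variance. An age spline reduced the mean standard error by 2.2–8.4%.

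**7. Chance age imbalance under random allocation.** The SD of the difference in mean age is 23.07 × √(1/8,100 + 1/9,900) = 0.35 years. In the central case one year of age difference moves the risk difference by 0.195 points. A 1-SD imbalance therefore moves it by 0.35 × 0.195 = 0.07 points, against a half-width of 0.575.

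**8. If age mix varied between dispatchers.** With 900 calls per dispatcher, age adds a design effect of 1 + 899 × R² × ICC to the unadjusted analysis. With linear age (R² = 0.053), the ratio of adjusted to unadjusted width is √[(1−0.053)/(1 + 899 × 0.053 × ICC)]. The interval would be about 5% narrower at an age ICC of 0.001, about 12.5% at 0.005 and about 20% at 0.01. The SAP gives no ICC.

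**9. ICU admission, for comparison.** At 2–4% with a weak age effect (odds ratio 1.1–1.3), the interval is 0.0–0.7% narrower.

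**The case against.** The strongest reply is that nothing here is wrong. Calls are said to be allocated at random, the variance is clustered by dispatcher, and the 95% interval already covers chance imbalance in age. That stands. An unadjusted risk difference or relative risk is a legitimate analysis under the stated design.

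A reader might go further and infer that the mortality comparison is biased by age. The SAP does not support this. The unequal call volumes suggest that routing depends partly on who is free, but nothing links availability to patient age. A one-year difference in mean age would be unusual by chance: even with an age SD of 25 years and 7,200 calls per arm, the SD of the difference is 25 × √(2/7,200) = 0.42 years, so one year is about 2.4 SD.

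It can also be said that the gain is small and rests wholly on assumed rates, that exact age for every call is inferred from the under-15 split, and that mortality might be analysed by Cox regression. All of this is fair. If Cox regression were used, the unchanged estimand could not be claimed, because a hazard ratio is not collapsible. The fix therefore has to settle the outcome type as well. What survives is that the improvement is real in direction, nearly free, and could still be fixed before the data were seen.

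**Conclusion.** The point holds as a missed gain in precision for 30-day mortality. Under the assumed mortality and age effects, the risk-difference interval would be about 0.3–10% narrower, and about 3–4% in the central case. The low end applies if age predicts death weakly or deaths are few; the high end needs 6% mortality and an odds ratio of 2.4 per 10 years. Larger gains require age mix to differ between dispatchers, which is possible but not shown.

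Three broader readings should be resisted. The plan is not biased under its stated allocation. ICU admission ("The number of participants needing an ICU admission at hospital") would gain next to nothing if age predicts it weakly. The SAP lists both as ordinary secondary outcomes and does not label either as a safety endpoint. Nor does the point extend to CPC and mRS: their ordered logistic odds ratios would become conditional on age, so the argument that the estimand is unchanged does not apply.

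**What to change.** Before data extraction, add to section 3.6:

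> *Death within 30 days is analysed as a binary outcome. The linear (RD) and Poisson (RR) models include patient age as a restricted cubic spline, with variance clustered by dispatcher. Missing age is imputed as described in section 3.7. Unadjusted estimates are reported alongside.*

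No further calls are needed. The cost is this short addition to the SAP, one more model term and reliance on age being recorded for most calls. The SAP does not document that, so the completeness of age should be reported. If extraction has already taken place, the adjusted analysis should be labelled as added afterwards and given as supporting.
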